## 5.0 STUDY TREATMENTS

### 5.1 Treatments Administered

ANB020 is a humanized IgG1/kappa mAb and was selected from a panel of mouse mAb humanized by complementarity-determining region-grafting, optimized and matured via mammalian cell display and somatic hyper mutation using AnaptysBio's (SHM)-XEL™ system to achieve a desired functional inhibitory potency.

ANB020 will be administered to patients by IV infusion in polyvinyl chloride or polyolefin bags following dilution to a total volume of 100 mL with sterile normal saline (0.9% sodium chloride [NaCl]). Placebo will be administered by IV infusion as 100 mL sterile normal saline (0.9% NaCl). Infusions will be administered over 1 hour.

### 5.2 Identity of Investigational Product

ANB020 is manufactured by Patheon of Greenville, North Carolina, US under Good Manufacturing Practice (GMP) regulations. ANB020 is provided as a sterile clear to slightly opalescent solution in a glass vial for IV infusion and contains no preservatives.

The ANB020 vials must be refrigerated at 2°C to 8°C (36°F to 46°F) until the day of use. ANB020 vials may be stored at room temperature (>8°C to 25°C [46°F to 77°F]) in the undiluted and/or diluted state for up to 8 hours. The vials should remain in the bulk cartons during storage and until use to provide protection from light. Vial contents should not be frozen or shaken. They are intended for single-use only; therefore, any remaining solution should be discarded.

The placebo contains no active drug and will be sterile normal saline (0.9% NaCl) for infusion. The placebo will be procured from the pharmacy stock supply.

Table 5.1 provides an outline of the dosing schedule for the study.

**Table 5.1 Dosing Schedule**

Investigational product	Dosage form and strength	Manufacturer
ANB020	IV infusion: 300 mg/100 mL once on Day 1	Patheon

Abbreviation: IV = intravenous

### 5.3 Packaging and Labelling

Labels will be prepared in accordance with GMP and local regulatory guidelines.

All IPs should be kept in a secure place under appropriate storage conditions. The IP label on the packaging specifies the appropriate storage.

## **5.4 Method of Assigning Patients to Treatment Group**

This is a randomized, double-blind, placebo-controlled study. On Day 1, after verification that all inclusion and no exclusion criteria have been met, the patients will be randomized in a 1:1 ratio to ANB020 or placebo. As patients become eligible they will be assigned randomization numbers which will be used to assign the allocated treatment. The Sponsor, Investigator, and patients will be blinded to treatment assignment of ANB020 or placebo. Additional information can be found in the study manuals.

## **5.5 Selection of Doses in the Study**

A single IV infusion of 300 mg/100 mL of ANB020 or 100 mL placebo (0.9% NaCl) will be administered.

The dose of ANB020 selected for this study has provided complete inhibition of IL-33 induced cytokine release and has been administered safely in study ANB020-001.

## **5.6 Selection and Timing of Dose for Each Patient**

Patients will receive a single dose of ANB020 or placebo administered under supervision at the study center. The infusion will be administered at the rate of 100 mL per hour via a Baxter infusion solutions set (FNC2110; prime volume 16 mL) or equivalent followed by a 16 mL IV saline flush, at the same infusion rate, to ensure that no residual drug remains in the infusion line. No in-line filter is to be used. Infusions will be administered over 1 hour. The ANB020 or placebo infusion may be slowed or interrupted for patients experiencing infusion-related AEs.

## **5.7 Blinding/Unblinding**

### **5.7.1 Blinding**

This is a randomized, double-blind, placebo-controlled study with limited access to the randomization code. The IP and placebo will be identical in physical appearance. The Sponsor, Investigator, and patients will be blinded to treatment assignment of ANB020 or placebo. The unblinded pharmacy staff will be provided the randomization assignments to prepare the assigned IP for each patient.

## **5.7.2 Unblinding**

The investigator is responsible for ensuring treatment-blinding information is maintained for all subjects. Unblinding information is available at the site by the unblinded pharmacist and investigator in case of a medical emergency.

Unblinding of treatment assignment during the study is discouraged and should occur only if it is absolutely necessary to know what treatment the subject received. If the investigator deems identification of the study drug is necessary for the purpose of providing urgent subject care, and knowledge of the subject's treatment assignment (ANB020 or placebo) will alter subsequent care, the treatment code for the specific subject will be obtained. Prior to unblinding, the investigator or appropriate designee should attempt to contact the Sponsor's Medical Monitor to discuss the need to unblind a subject. In the event the Medical Monitor cannot be reached, the investigator should ensure that the unblinding of the treatment code is performed in a discrete manner and the treatment is disclosed only to those persons involved with the direct medical care of the subject. The investigator should contact the Sponsor's Medical Monitor immediately (within 24 hours including weekends) following emergency unblinding. Once the subject's treatment assignment has been obtained in the event of an emergency, the date, time, and reason for the unblinding must be recorded in the pharmacy log, on the subject's CRF and source notes and signed by the investigator.

## **5.8 Prior and Concomitant Treatments**

### **5.8.1 Excluded Medications**

The following medications will not be permitted during the study. Use of these excluded medications is a protocol deviation and should be recorded in the electronic case report form (eCRF).

- Treatment with systemic corticosteroids (intramuscular or oral) equivalent to >15 mg/day prednisone, nonsteroidal, immunosuppressant or immunomodulating drugs within 8 weeks before screening and throughout the study.
- Any antibiotic treatment within 4 weeks before screening.
- Use of biologics such as mepolizumab or omalizumab within 3 months or 5 half-lives (whichever is longer) before screening and throughout the study.
- Any live attenuated vaccine within 4 weeks of screening and for the duration of the study (Day 127).

### **5.8.1.1 Excluded Medications Prior to Lung Function Assessments**

Patients should withhold their usual asthma therapies prior to the lung function tests on the study visit days.

- Short-acting bronchodilators (e.g. albuterol [salbutamol] or ipratropium) should be withheld for at least 6 hours before spirometry.
- Twice daily long-acting bronchodilator (LABA or long-acting muscarinic antagonist [LAMA] containing therapies) should be withheld for 12 to 24 hours and once daily long-acting bronchodilator (LABA or LAMA containing therapies) for >24 hours before spirometry.
- Leukotriene receptor antagonists (LTRA) should be restricted for >24 hours.
- Twice daily theophyllines should be withheld for at least 12 to 24 hours and once daily theophyllines for >24 hours before spirometry.
- If a patient has taken rescue SABA within 6 hours of the planned spirometry study center visit, they should either:
  - a. remain at the center until the 6-hour withholding time has been reached or
  - b. return on the following day for lung function assessments (If the patient completed Day 22 visit, he or she can return within 2 days [allowed window period per protocol] for the lung function assessment).

### **5.8.2 Allowed Medications**

Use of high dose ICS plus LABA and systemic corticosteroids (intramuscular or oral) up to the equivalent of 15 mg/day prednisone will be allowed in the study.

High dose guidelines are as follows:

- Beclomethasone dipropionate (chlorofluorocarbon [CFC]) High: >1000 µg
- Beclomethasone dipropionate (hydrofluoroalkane [HFA]) High: >400 µg
- Budesonide (dry powder inhaler [DPI]) High: >800 µg
- Ciclesonide (HFA) High: >320 µg
- Fluticasone furoate (DPI) High: 200 µg
- Fluticasone propionate (DPI or HFA) High: >500 µg
- Mometasone furoate High: >440 µg

- Triamcinolone acetonide: >2000 µg

Specific treatment for asthma exacerbations will be allowed at the Investigator's discretion. Oral prednisolone and or antibiotics will be allowed at the discretion of the treating physician.

Administration of the inactivated flu vaccine will be allowed. Females of childbearing potential are to continue using their hormonal contraceptives and postmenopausal women are allowed to use hormone replacement therapy.

The Investigator must record the use of all concomitant medications, both prescribed and over-the-counter, into the eCRF and patient's medical records. This includes medications used on both a regular and an as needed basis. Patients should be discouraged from starting any new medication, both prescribed and over-the-counter, without consulting the Investigator, unless the new medication is required for emergency use or has been prescribed for clinical need.

## **5.9 Medical Care of Patients after End of Study**

All patients will return to the study center for the EOS (Day 127) or ET visit for final safety and EOS assessments. After this visit, patients should be treated according to the Investigator's clinical judgment. Care after EOS/ET will not be provided by AnaptysBio. Any significant AE which in the opinion of the Investigator is related to the IP, SAE, or pregnancy occurring within 30 days after the EOS visit should be reported to the safety team at IQVIA and followed up until final outcome or stabilization.

## **5.10 Treatment Compliance**

The prescribed dosage, timing, and mode of administration may not be changed. Any deviations from the intended regimen must be recorded in the eCRF. Infusion start date/time and infusion end date/time will be documented in the patient's eCRF. Any infusion interruptions (stop date/time and restart date/time) and/or incomplete dose administration will also be documented.

## **5.11 Investigational Product Accountability**

The Investigator, a member of the investigational staff, or a hospital pharmacist must maintain an adequate record of the receipt and distribution of all the IPs using the Drug Accountability Form. These forms must be available for inspection at any time.

All the IP supplies should be accounted for at the termination of the study and a written explanation provided for discrepancies. All unused IP supplies and packaging materials are to be inventoried and returned to IQVIA/AnaptysBio by the Investigator or may be destroyed on site following institutions standard operating procedures (SOPs) and proper accountability by IQVIA

site monitor. The Investigator is not permitted to return or destroy unused IP supplies or packaging materials unless authorized by IQVIA.

## **6.0 STUDY PROCEDURES**

Study procedures will be performed as detailed in the Schedule of Events in Table 4.1.

Assessments scheduled on the day of IP administration must be performed prior to the IP infusion unless otherwise noted. All assessments will be performed on the day of the specified visit; however, a window period of +/-2 days can be implemented following the Day 22/Week 3 visit.

There are visits where the protocol requires more than one procedure to be completed at the same time point. When indicated, the procedure must follow specific order of events, refer to Section 6.2.6 for instructions.

Study team must verify that patients withheld their usual asthma therapies prior to the lung function tests on each study center visit day. See Section 5.8.1.1 for the details.

### **6.1 Screening**

Each potential patient will provide informed consent at screening before starting any study related procedures. The eligibility of patients will be determined during the screening period. Vital signs, physical examinations, medical history, and ongoing medications will be recorded. Other screening procedures will be carried out in accordance with the Schedule of Events in Table 4.1.

#### **6.1.1 Fractional Exhaled Nitric Oxide (FeNO) Test**

Measurement of FeNO will be performed at the time points indicated in Table 4.1 and in accordance with the guidelines published by American Thoracic Society/European Respiratory Society (ATS/ERS). The FeNO test must be performed before the spirometry testing. Details about the FeNO measurement are provided in the pulmonary function testing manual provided by the manufacturer.

#### **6.1.2 Spirometry (FEV1 Measurement)**

Spirometry will be performed at the time points indicated in Table 4.1 and according to the ATS/ERS guidelines. The spirometer should be calibrated per ATS/ERS guidelines prior to the start of the lung function assessment on each study center visit day. The spirometer should be set to use the Global Lung Function Initiative reference equations.

Both pre- and post-bronchodilator spirometry should be performed at all clinic visits. Pre-bronchodilator spirometry will be performed after appropriate bronchodilator withholding period

(See Section 5.8.1.1) in the morning and post-bronchodilator spirometry will be performed 30 minutes following the administration of 400 µg salbutamol via a Volumatic.

Patients should have spirometry performed at approximately the same time on each study center visit day. Forced expiratory maneuvers should be performed with the patient seated in an upright position. If this is not comfortable for the patient, standing is permitted; however, the same position should be used by the patient for each forced expiratory maneuver from screening through EOS visit. Three acceptable maneuvers should be obtained for each test. Additional details are provided in the pulmonary function testing manual provided by the manufacturer.

### **6.1.3 Asthma Control Questionnaire**

The ACQ (See Section 13.0) will be used in this study to assess the asthma symptoms (night-time waking, symptoms on waking, activity limitation, shortness of breath, wheezing, and SABA usage) along with the FEV1 measurement.

Patients will be asked to recall their experiences during the previous week by responding to 5 symptoms related questions and 1 question related to bronchodilator use. Questions will be scored from 0 (totally controlled) to 6 (severely uncontrolled). The questionnaire will be completed at each study center visit except Day 2 visit (See Table 4.1) and must be completed prior to blood draw/laboratory assessments and other procedures such as FeNO and FEV1. Refer to section 6.2.6 and Table 4.1 for timings and instructions.

### **6.1.4 Patient Diary**

The patient diary will be distributed during each study center visit day (except EOS visit) and all patients will be trained to record the asthma symptoms and other details in the diary on a daily and weekly basis as listed below. All patients will be asked to return the diary cards when they come for the next study center visit and the study team will review the patient diary cards (from previous weeks) during each study center visit for completeness. (If the patient does not meet inclusion/exclusion criteria the diary card will not be collected).

The following details will be recorded in the patient diary on a daily and weekly basis.

#### Daily Recording

- Number of puffs that the patient needed to use their rescue (SABA) medication during the day.

### Weekly Recording

- List asthma symptoms experienced during the week: wheezing, cough, shortness of breath, chest tightness, or describe other.
- Change in SOC treatment.
- Study treatment efficacy (after Day 1).
- Level of satisfaction with the side effects related to the study treatment (after Day 1).
- PGIC (after Day 1).
- Hospitalization due to asthma.

## **6.2 Study Day Procedures**

### **6.2.1 Blood volume**

The total blood volume for each patient will be approximately 295.5 mL, and within the National Institute of Health allotted amounts of 550 mL in any 8-week period.

### **6.2.2 Day 1 (Randomization)**

On Day 1, study staff will confirm the informed consent and patient's willingness to participate in the study. The patients will be randomized to receive either ANB020 or placebo in a 1:1 ratio (12 patients will receive ANB020 and 12 patients will receive placebo). Additional Day 1 procedures will be carried out in accordance with the Schedule of Events in Table 4.1.

Patients will be allowed to leave the study center 6 to 8 hours after the ANB020/placebo administration and completion of study-specific procedures providing that:

- No AEs have been reported during the study visit.
- The patient responds in the affirmative when asked if they are feeling well.

If any of these conditions are not met, then the patient will only be allowed to leave the study center with the authorization of the Investigator or appropriately qualified delegate.

### **6.2.3 Follow-up Period**

After completing the Day 1 assessments, all patients will be in the follow-up period for 18 weeks. During the 18-week follow-up period, the patients will return to the study center for various assessments on Day 2, 8, 22, 36, 64, 85, and 106 and will be contacted via telephone by

study staff on Day 50 and 57. The study procedures will be carried out in accordance with the Schedule of Events in Table 4.1.

### **6.2.3.1 Patient Global Impression of Change (PGIC)**

The PGIC scale (See Section 14.0) will be used for an overall evaluation of response to treatment. The patient will be asked to rate the degree of change in the overall asthma status compared to the start of treatment, i.e. Day 1. A 7-point rating scale will be used as listed below:

1 = very much improved, 2 = much improved, 3 = minimally improved, 4 = no changes, 5 = minimally worse, 6 = much worse, and 7 = very much worse.

Refer to Table 4.1 for instructions.

### **6.2.3.2 Investigator's Assessment-Clinical Global Impression of Change (CGIC)**

The CGIC scale (See Section 15.0) will be used for an overall evaluation of response to treatment. The Investigator will be asked to rate the degree of change in the overall asthma status compared to the start of treatment, i.e. Day 1. A 7-point rating scale will be used as listed below:

1 = very much improved, 2 = much improved, 3 = minimally improved, 4 = no changes, 5 = minimally worse, 6 = much worse, and 7 = very much worse.

The CGIC should be completed prior to blood draw/laboratory assessments and other procedures such as FeNO and FEV1. The time points are indicated in the Schedule of Events in Table 4.1. Refer to section 6.2.6 and Table 4.1 for timings and instructions.

It is recommended that the same Investigator/Sub-Investigator completes the scale for all time points for a given patient.

## **6.2.4 End of Study**

All patients will return to the study center for the EOS visit on Day 127 (Week 18). The EOS procedures will be carried out in accordance with the Schedule of Events in Table 4.1.

## **6.2.5 Early Termination**

Patients who discontinue the study early will be asked to return to the study center for the ET procedures as shown in the Schedule of Events (Table 4.1). The ET visit will include all procedures to be done at EOS visit as well as any other laboratory assessment (PK or ADA) planned at the originally scheduled follow-up visit.

## 6.2.6 Timing of Procedures

There are visits where the protocol requires more than one procedure to be completed at the same time point. In these instances, the following will apply:

- All safety assessments will be timed and performed relative to the start of IP administration.
- Blood draw: Lab-flow document should be followed for standardized order of blood draw collection. If entire panel is unable to be collected, hematology panel (eosinophils) will take precedence over other tests.
- Study specific scales and questionnaire forms should be completed prior to blood draw/laboratory assessments and other procedures such as FeNO, FEV1.
- FeNO must be performed before FEV1.

On Day 1, ACQ, safety laboratory tests, urine pregnancy (confirm negative), ADA, IFN- $\gamma$ , cytokines, FeNO, and FEV1 (both pre- and post-bronchodilator) must be completed prior to IP administration. The PK samples will be collected prior to IP administration as well as post-dose on Day 1. Refer to Table 4.1 (Schedule of Events) and Section 18.0 (Appendix VI) for additional details.

## **7.0 SAFETY, PHARMACODYNAMIC, AND PHARMACOKINETIC ASSESSMENTS**

### **7.1 Safety**

Safety assessments will be based on medical review of AE reports, the results of physical examinations, and clinical laboratory tests. The incidence of observed AEs will be reviewed for potential significance and clinical importance. Patients with any ongoing AEs or SAEs at the time of scheduled discharge from the study center, should remain at the study center until the Investigator has determined that these events have been resolved or deemed as not clinically significant.

#### **7.1.1 Adverse Events**

The Investigator is responsible for recording all AEs observed during the study period.

Definition of AE: An AE is any untoward medical occurrence in a patient or clinical investigation patient administered a pharmaceutical product and which does not necessarily have a causal relationship with this treatment.

Definition of SAE: An SAE, experience or reaction, is any untoward medical occurrence (whether considered to be related to the IP or not) that at any dose:

- Results in death.
- Is life-threatening (the patient is at a risk of death at the time of the event; it does not refer to an event which hypothetically might have caused death if it were more severe).
- Requires inpatient hospitalization or prolongation of existing hospitalization: Hospital admissions and/or surgical operations planned before or during a study are not considered AEs if the illness or disease existed before the patient was enrolled in the study, provided that it did not deteriorate in an unexpected way during the study.
- Results in persistent or significant disability/incapacity.
- Is a congenital abnormality/birth defect.
- Other: Medically significant events, which do not meet any of the criteria above, but may jeopardize the patient and may require medical or surgical intervention to prevent one of the other serious outcomes listed in the definition above. Examples of such events are

blood dyscrasias (e.g. neutropenia or anemia requiring blood transfusion, etc.) or convulsions that do not result in hospitalization.

An adverse drug reaction (ADR) is defined as all noxious and unintended responses to a medicinal product related to any dose.

An unexpected ADR is defined as any adverse reaction, the nature of which is not consistent with the applicable product information.

Each AE is to be evaluated for duration, severity, seriousness, and causal relationship to the IP. The action taken and the outcome must also be recorded.

### **Severity**

The severity of the AE will be characterized as “mild, moderate, or severe” according to the following definitions:

- Mild events are usually transient and do not interfere with the patient’s daily activities.
- Moderate events introduce a low level of inconvenience or concern to the patient and may interfere with daily activities.
- Severe events interrupt the patient’s usual daily activity.

### **Relationship**

The causal relationship between the IP and the AE has to be characterized as unrelated, unlikely, possible, probable, or unknown (unable to judge).

Events can be classified as “unrelated” if there is not a reasonable possibility that the IP caused the AE.

An “unlikely” relationship suggests that only a remote connection exists between the IP and the reported AE. Other conditions, including chronic illness, progression or expression of the disease state or reaction to concomitant medication, appear to explain the reported AE.

A “possible” relationship suggests that the association of the AE with the IP is unknown; however, the AE is not reasonably supported by other conditions.

A “probable” relationship suggests that a reasonable temporal sequence of the AE with drug administration exists and, in the Investigator’s clinical judgment, it is likely that a causal relationship exists between the drug administration and the AE, and other conditions (concurrent illness, progression or expression of disease state, or concomitant medication reactions) do not appear to explain the AE.

All efforts should be made to classify the AE according to the above categories. The category “unknown” (unable to judge) may be used only if the causality is not assessable, e.g. because of insufficient evidence, conflicting evidence, conflicting data, or poor documentation.

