#### ***7.1.1.2 Reporting of Serious Adverse Events to Regulatory Authorities and Investigators***

All SAEs that are considered unexpected and related to the IP will be reported by IQVIA as a 15-Day report to the regulatory authorities as applicable and to all participating Investigators.

The SAEs that are considered unexpected, related to the study and are life-threatening or result in death will be reported by IQVIA to the regulatory authorities as applicable, and to all participating Investigators as a 7-Day report. IQVIA will ensure that all SAEs are reported to the appropriate regulatory authorities.

Investigators will be notified by IQVIA of all SAEs that require prompt submission to their Independent Ethics Committee (IEC). Each Investigator must notify the IEC responsible for reviewing the study at their site of all 15-Day or 7-Day safety reports required by local regulations or IEC requirements and should provide written documentation of IEC notification for each report to IQVIA. This study will comply with all local regulatory requirements and adhere to the full requirements of International Council for Harmonisation (ICH) Guideline for Clinical Safety Data Management, Definitions and Standards for Expedited Reporting, Topic E2.

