18.1. ADVERSE EVENTS

AEs will be coded using MedDRA version 19.1.

Treatment emergent adverse events (TEAEs) are defined as AEs that started or worsened in severity on or after the date and time of the study drug infusion.

Non-treatment emergent adverse event (Non-TEAE) will be defined as any AE that started on or after the date of informed consent and before the administration of study drug.

AEs with missing start dates will be considered treatment-emergent. AEs with missing stop dates or

Document: \\ieedc-vnasc01\biosdata\AnaptysBio\ANB020\CYA74392\Biostatistics\Documentation\SAP\Final\20181218 \\
Author: \quad \text{Version Number:} \quad 1.0

Version Date: 18Dec2018

Template No: CS_TP_BS016 Revision 4 Reference: CS_WI_BS005

Effective Date: 01Apr2016

AnaptysBio, ANB020 CONFIDENTIAL

IND 126765, SN 0035

Clinical Study Report ANB020-004 - Original

AnaptysBio Inc PROTOCOL ANB020-004 Page 29 of 46

IQVIA STATISTICAL ANALYSIS PLAN

with stop dates after the end of the study date will be considered to have been ongoing at the end of the study.

The severity of AEs will be characterized as "mild, moderate, severe" according to the following definitions:

Mild events are usually transient and do not interfere with the patient's daily activities

Moderate events introduce a low level of inconvenience or concern to the patient and may interfere with daily activities

Severe events interrupt the patient's usual daily activity

Missing severity will be assumed to be the worst severity case i.e. 'severe'; however, in the listing, it will be displayed as missing.

The causal relationship between the study drug and the AE will be characterized as "Unrelated, Unlikely, Possible, Probable, and Unknown (unable to judge)".

The summaries will be presented as "Related" versus "Not Related".

Categories "Unrelated" and "Unlikely" will be mapped to "Not Related", while the categories "Possible", "Probable" and "Unknown" will be mapped to "Related".

Missing relationship will be assumed to be the worst severity case i.e. 'Related; however, in the listing, it will be displayed as missing.

An overview of adverse event along with the number and percentage of patients experiencing TEAEs, for each treatment group will be provided.

If patient has multiple TEAEs by severity and/or multiple relationship with study drug, worst case severity and the worst-case relationship to the study drug will used for overview tabulation.

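### The causality scale has no clean category for an adverse event that both the drug and the asthma could explain, so the same event can be reported as Related or Not Related

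*Protocol*

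**What the plan says.** Protocol 7.1.1 (Relationship) has four graded categories and a residual one.

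- *Unrelated* applies "if there is not a reasonable possibility that the IP caused the AE".
- *Unlikely* has two parts. The first is that the "relationship suggests that only a remote connection exists between the IP and the reported AE"; the definition then adds: "Other conditions, including chronic illness, progression or expression of the disease state or reaction to concomitant medication, appear to explain the reported AE".
- *Possible* means that "the association of the AE with the IP is unknown; however, the AE is not reasonably supported by other conditions".
- *Probable* needs a reasonable time sequence, a judgement that a causal link is likely, and that other conditions, with the disease state and other medicines named among them, "do not appear to explain the AE".
- *Unknown* is reserved for causality that cannot be assessed, conflicting evidence being one listed reason, and only after every effort to use the other four.

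SAP 18.1 collapses the scale to two levels. Unrelated and unlikely become Not Related; possible, probable and unknown become Related. A missing assessment also counts as Related. The footnote to Table 14.3.1.6 in the table shells gives the same mapping of the five categories.

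Protocol 7.1.1.2 makes expedited reporting depend on relatedness: "All SAEs that are considered unexpected and related to the IP will be reported by IQVIA as a 15-Day report". It does not say which of the five categories count as related.

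**The concern.** Both categories that affirm a link exclude events with a competing explanation. The only graded category whose wording accepts one is *unlikely*, which the SAP reports as Not Related.

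The overlap is built into this population. Protocol 2.4 names wheezing and difficulty breathing among the symptoms of an allergic reaction to a drug. Protocol 2.1 lists wheeze, shortness of breath and chest tightness as features of asthma, which every patient has. Events with two reasonable explanations are therefore to be expected.

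Safety and tolerability is a primary objective (protocol 3.1). Relatedness feeds the related-TEAE row of Table 14.3.1.1, the whole of Table 14.3.1.6, and the expedited-reporting triggers. Protocol 7.1.1.1 also asks for a causality assessment at the first notification of an SAE, when alternative causes are least resolved.

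**Working it through.** The plan gives no figure on this point, so the check is one of logic. Take an event that the product and the asthma could each reasonably explain, such as wheeze after the infusion, and test it against each definition in protocol 7.1.1.

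| Category | What the definition needs | Does the event meet it? | Level in SAP 18.1 |
|---|---|---|---|
| Unrelated | No reasonable possibility that the product caused it | No: there is such a possibility | Not Related |
| Unlikely | (a) Only a remote connection, and (b) other conditions appear to explain it | (a) No, (b) yes | Not Related |
| Possible | No reasonable support from other conditions | No: the asthma supports it | Related |
| Probable | Likely causal, and other conditions do not appear to explain it | No: the asthma appears to explain it | Related |
| Unknown | Causality cannot be assessed, after all efforts to use the other four | Only if the investigator treats two plausible causes as conflicting evidence | Related |

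1. No graded category fits. The nearest is *unlikely*, with one of its two parts met.
2. Two ways out remain: *unlikely*, reported as Not Related, or *unknown*, reported as Related. The documents do not determine which.
3. The scale's own boundaries do not meet. *Unrelated* ends where a reasonable possibility begins. *Possible* does not begin there; it begins only once other explanations have been set aside.
4. The SAP sharpens the contrast. An event with no causality assessment is counted as Related, while one assessed as having two plausible causes can be counted as Not Related.

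Scale: protocol 6.2.2 plans 12 patients per arm. One patient is 1/12 = 8.3 percentage points, so a single patient who changes category visibly moves a row of the related-TEAE table. How many would do so cannot be derived, because the documents give neither adverse event rates for this trial nor the share of events with a competing explanation.

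**The case against.** Several points on the other side are sound.

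**Classification.** A reader might infer that every event with two causes goes to *unlikely* and so to Not Related. The text does not say that. *Unlikely* also needs a remote connection, and *unknown* offers a restricted route to Related. What stands is a gap filled by individual judgement.

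**Expedited reporting.** A reader might infer that unexpected SAEs will be kept out of the 15-day and 7-day reports. That is not shown. Protocol 7.1.1.1 sends SAEs from consent through the defined follow-up to IQVIA within 24 hours whatever their judged relationship. Protocol 7.1.1.2 commits to the full ICH requirements on expedited reporting and does not make the investigator the only judge. A Safety Plan that is not among these documents may cover the rest. What stands is that 7.1.1.2 depends on a relatedness judgement made on an incomplete scale, without saying how the categories translate.

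**Safety conclusions.** The main TEAE, serious TEAE, discontinuation and death tables ignore causality and are shown against a randomized placebo arm. Investigators are blinded, so a coding habit should affect both arms. Asthma exacerbations are counted separately whatever their cause. There is no data monitoring committee (protocol 7.1.4), but SAP 4.2 and 21 plan two restricted unblinded reviews that include adverse events. All of this limits the damage. None of it repairs the tables that use relatedness.

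**Size.** A reader might take the 44% of Phase I subjects with drug-related events (protocol 2.4), compute 0.44 × 12 = 5.3 patients per arm, and assume that some fraction of them move. The inputs do not support that. The rate comes from healthy volunteers without asthma, under a causality scale that the documents do not give, and the fraction would be invented. A fraction of events is also not a fraction of patients. SAP 18.1 counts each patient at the worst relationship, so a patient leaves the Related count only if every one of that patient's related events is reclassified.

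**Conclusion.** The point holds as a defect in the definitions. The four graded categories leave no clean place for an event that drug and disease could both explain, and such an event can end as Related or Not Related depending on the investigator. The related-TEAE tables can therefore be under-counted, and inconsistent between centers (up to 6 in the protocol synopsis, 7 in SAP 7.2). The judgement behind expedited reports may be affected, but the documents do not show that any report would be missed.

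The size cannot be computed. The conclusion assumes that investigators apply the definitions as written and that events with two reasonable explanations occur. The overlap between the asthma symptoms and the allergic-reaction symptoms in the protocol makes the second assumption reasonable. The definition should be changed, since it bears on a primary objective and the remedy is a matter of wording.

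**What to change.** - In protocol 7.1.1, define *possible* as: a causal contribution of the product is a reasonable possibility, whether or not other conditions could also explain the event. This is the standard that the protocol already uses, in the negative, for *unrelated*.
- Keep *unlikely* for events with only a remote connection to the product.
- Keep the SAP 18.1 mapping, and state in protocol 7.1.1.2 that it also governs expedited reporting: possible, probable and unknown count as related.
- Leave the 7-day sentence of 7.1.1.2 unchanged. It refers to a relationship with the study, which can be read as broader than a relationship with the product. Aligning it with the 15-day sentence could narrow that trigger.

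The cost is wording in the protocol and in the eCRF guidance. Somewhat more events would be counted as related, and there may be an extra expedited report.
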